7.2 Planned recruitment rate

We estimate a single centre to open for the first 4 months, then recruit one centre a month until there are 25 (over 28 months). When open, the average recruitment per centre per month will be 0.7 participants.

At 18 months we expect 15 centres open, and 86 participants randomised. At the end of the internal pilot phase (at 18-months), the number of sites open to recruitment, recruitment rates and adherence to allocated treatments will be assessed

Red, amber and green outcomes will be set for recruitment, site opening and data completion. The outcome will be judged as RED if centres have recruited less than 30 participants which equates to less than 35% of the projected numbers at this stage; AMBER if centres have recruited 30-85 participants which equate to 35- 100% of the projected numbers at this stage; and GREEN if centres have recruited over 86 participants which equate to >100% of the projected numbers at this stage. At the end of the internal pilot the number of centres actively recruiting; data completion and visit completion at 6-weeks will be assessed in the same way.

Progression Criteria	Red	Amber	Green
Number recruited	<30 participants	30-86 participants	>86 participants
Number of sites opened	<5	5-15	>15
Data completion	<70%	70-85%	>85%
6-week clinical follow up completed	<70%	70-85%	>85%

Table 1: Progression criteria after 18 months of recruitment to the EARNEST trial generated using the internal pilot.

Predicted recruitment is 470 participants in the UK over 42-months, an average of 135 patients/year (we estimate this will be 1 in 4 patients with acute uTBAD presenting to sites).

Confidential Page 34 of 30

EARNEST	Protocol No:	Spansari	Imperial	Collogo	V1.0 7 th Oct 2024
EARNEST	174766	Sponsor: London	imperiai	College	V1.0 7 OCI 2024

7.3 Statistical Analysis

Statistical analysis is the responsibility of [name] at LSHTM. The analysis and reporting will conform to the standards set by the Consolidated Standards of Reporting Trials statement.[22] Analysis will be undertaken guided by a pre-specified Statistical Analysis Plan (SAP), which will be approved by the TSC, prior to database lock. Any deviations from the SAP will be justified and documented in the final report.

(i) Analysis populations

Primary statistical analysis will be based on the intention to treat principle. Participants will remain in the study from randomisation to end of follow up and be analysed in the group to which they were randomised. This primary analysis will take place when all participants are at least 5 years post-randomisation.

An interim analysis will take place at one year after randomisation to report the outcomes of the TEVAR procedure (complication rates and early outcomes). There will be no formal assessment of the need to stop the trial on the basis of efficacy at this stage. No other interim analyses for efficacy will be undertaken.

(i) Primary Endpoint Analysis

An independent outcome adjudication committee working to strict protocols will review all reported primary endpoints using source data.

Times from randomisation to the first primary outcome component will be summarised using Kaplan-Meier estimates. Participants who do not have an event or are lost to follow up (including due to intercurrent events such as non-aortic death) will be censored at last visit. This has been termed the Hypothetical Strategy estimand, since it assumes that people who are censored would have had the same risk as those who are not censored, if they had remained in the study. The estimand for our primary analysis is the hazard ratio for the comparison between TEVAR and BMT, estimated from a Cox proportional hazards model (after checking the model assumptions) adjusting for minimisation variables age and sex as fixed effects and centres as random intercepts. The treatment hazard ratio, 95% confidence interval and Wald p-value will be reported.

(ii) Secondary Endpoints Analysis

- Similar survival model methods will be used for secondary time to event outcomes, including aortic-related mortality, all-cause mortality and reinterventions.
- The number of complications each participant experiences will be analysed using negative binomial models, with patient as the random effect, treatment arm and the minimisation factors as fixed effects and adjusting for time at risk.
- Rate of aortic remodelling between TEVAR+BMT+SURV and BMT+SURV groups will be analysed by the core lab. CT angiograms at presentation of the index event, six weeks post TEVAR/or after dissection and one year will be analysed by the core lab according to a standard protocol. The rate of false lumen thrombosis and

Confidential Page 35 of 30

EARNEST	Protocol No: 174766	Sponsor: London	Imperial	College	V1.0 7 th Oct 2024

maximum diameter/area of false lumen, true lumen and whole aorta as well as ratios will be compared between groups.

 Patient reported outcomes measured over time, including the index value from the EQ-5D-5L, will be analysed using linear mixed models. We will first decide on the most appropriate covariance structure. This means starting with a saturated mean model (including treatment, age, sex, baseline index value and all interactions) and exploring patient-specific random intercepts, random slopes and their correlations. After fixing this covariance structure, we force treatment, age and sex into the model, assuming a constant treatment effect over time. This again reflects a hypothetical strategy estimand for the treatment effects at each time point.

(iii) Safety

All Serious adverse events will be reported by treatment arm, stratified by severity, relationship to treatment/trial conduct whether or not they are expected. Statistical monitoring of safety data by ICTU will be conducted throughout the trial and reported at agreed intervals to the DMEC.

(iv) Exploratory analysis

- We will explore the relationship between initial aortic diameter and changes over time through estimation of the correlation between random intercepts and random slopes (covariance structure).
- We will explore the effects of other baseline measurements and CT criteria and their interactions with treatment arm, on long-term aortic growth.
- Further exploratory analysis may be undertaken should it be warranted.

(v) Sensitivity Analysis

For technical details of the following sensitivity analysis, see the SAP.

- In addition to the above ITT analysis, a per-protocol population (PP) will also be defined, which will include all eligible randomised participants according to the treatment received but will exclude major protocol violations. Results from both the ITT and the PP analyses will be presented.
- In an RCT, we do not expect substantial amounts of missing baseline measurements. Therefore, the primary analysis will include complete cases only. However, analysis of the primary outcome and key secondary outcomes could be repeated after using Chained Equations to impute missing baselines multiple times, with resulting estimates of the treatment effects combined using Rubin's rules. This method will be used if more than 10% of cases have some missing baseline data. The method assumes that the incomplete baselines are Missing at Random conditional on measurements that are observed, an untestable assumption.
- The primary outcome analysis assumed non-informative censoring for those participants who did not have the primary outcome during follow up. We will repeat the analysis using inverse probability of censoring weights to adjust for differences between fully observed and censored survival times.

Confidential Page 36 of 30

EARNEST	Protocol No:	Sponsor:	Imperial	College	V1.0 7 th Oct 2024
	174766	London			

- We will consider sub-distribution hazard ratios for the primary outcome to adjust for competing risks such as death from non-aortic causes.
- Other sensitivity analyses will be completed should the trial data or analysis be deficient in another way.

(vi) Cost effectiveness

Cost-utility analysis will consider NHS and personal social services (PSS) costs including productivity losses due to sick leave. The outcomes will be presented as incremental cost per Quality Adjusted Life Year (QALY) gained.

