1.9 Summary Table of Endpoints

Endpoints	Timepoint(s) of evaluation of this endpoint

Confidential Page 17 of 30

EARNEST	Protocol No:	Sponsor:	Imperial	College	V1.0 7 th Oct 2024
	174766	London			

	174766	London					
Primary	Time to first related mort AND/OR ser permanent r deficit AND/opermanent cardiorespira	ality vere neurological OR severe	Throughout follow up from randomisation until the first composite event. Patients censored if there is a competing event (non-aortic-related death, patient withdrawal or end of the study). Reported when all patients are five years after randomisation.				
Secondary Aortic-related mortality		until the aortic-recensored if there (non-aortic-relate withdrawal or enwhen all patients year for the TEV.	w up from randomisation elated death. Patients is a competing event ed death, patient d of the study). Reported have completed one AR group and five years ion for all patients.				
	All-cause mo	ortality	until death from a when all patients year for the TEV	w up from randomisation any cause. Reported have completed one AR group and five years ion for all patients.			
	Complication stroke, para cardiorespira	plegia and	patients have co	w up. Reported when all mpleted one year for the nd five years after or all patients.			
	Reinterventi	ons		w up. Reported when all mpleted one and five omisation.			
QoL			allocation, and a months and then randomisation ur	seline prior to group t 6 weeks, 6 months, 12 a annually from ntil the end of follow up. essed using EQ-5D-5L			
	Aortic remod	delling	measured using	TEVAR in the pand at five years CT/MRI scans assessed ranalysis protocol from			

Confidential Page 18 of 30

EARNEST	EARNEST Protocol No: 174766		Imperial	College	V1.0 7 th Oct 2024	
		Health resource use and costs will be measured across follow up assessments and will be analysed at 5 years				
	Cost-effectiveness.		Health resource use and costs will be measured across follow up assessments and will be analysed at 5 years			
	blood	Blood possible baseline 6 weeks annually	ressure we prior to go, 6 month	vill be recorded at group allocation, and at as, 12 months and then adomisation until end of alysed at 5 years.		

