2. STUDY DESIGN

2.1 Design

EARNEST is a multicentre, open label, superiority RCT, allocating consenting patients with uTBAD in the sub-acute phase in a 1:1 ratio to TEVAR and BMT and surveillance (TEVAR+BMT+SURV) or BMT and surveillance (BMT+SURV). It will have adjudicated endpoints and an internal pilot. Each patient will be followed up for a minimum of 5-years.

Patients with uTBAD in the sub-acute phase (from 10 days to 3 months after the aortic dissection occurs) will be identified at vascular centres and regional network hospitals. After consent, participants will be allocated in a 1:1 ratio to TEVAR and BMT (TEVAR+SURV+BMT) or BMT and surveillance (BMT+SURV) using a using a minimisation algorithm, incorporating a random element, to ensure groups are well balanced for centre, age and sex. We refer to this as randomisation.

Those in the TEVAR+BMT+SURV group will undergo the intervention, TEVAR, at 25 specialist vascular sites in the UK. To ensure the highest standards of care and consistency across all participating centres in the clinical trial of Thoracic Endovascular Aortic Repair (TEVAR) for Type B Aortic Dissection (TBAD), a credentialing process will be implemented. This process will assess each centre's capability, infrastructure, and experience in performing TEVAR for uTBAD, ensuring compliance with established guidelines and standards.

Criteria for Credentialing for Participating Centres:

- 1. Multidisciplinary Team (MDT) and compliance with standard procedures:
- Centres must have an established MDT experienced in managing TBAD cases, including vascular surgeons, interventional radiologists, cardiologists, and specialist nurses.
- The MDT must demonstrate compliance with the "Provision of Vascular Services" document distributed by the Vascular Society of Great Britain and Ireland (2021).
- 2. Infrastructure and Facilities:

Confidential Page 19 of 30

EARNEST	Protocol No:	Sponsor:	Imperial	College	V1.0 7 th Oct 2024
	174766	London	por.u.	ooogo	

- Centres must provide comprehensive details of the unit's infrastructure and available facilities for the treatment of TBAD patients, including endovascular suites, post-operative care facilities, and availability of advanced imaging technologies.
- 3. Standard Operating Procedures (SOPs) and Service Provision:
- Centres must submit their SOPs and detailed documentation of their uTBAD patient care pathways, including pre-operative, intra-operative, and post-operative management protocols.

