All patients will be seen at 6-weeks, 6-months, one year and yearly (to five years after enrolment) when clinical and cost-effectiveness data will be collected. Both groups will undergo CT/MRI assessment at one year and yearly (to five years after enrolment).

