4.4 Visit Schedule

Visit	0	1	2	3	4	5-9
	Screening	Consent	FOR TEVAR+BMT+ SURV only TEVAR Intervention	Clinical and research assessment	Clinical and research assessment	Clinical and research assessment
TIMEPOINT	Within 3 months of index uTBAD	After the requirement for intensive care or high dependency care has ended, and the patient has not received opiate analgesia for at least 48 hours and from 10 days to 3 months of	10 days-3 months after index uTBAD	FOR BMT+SURV 6 weeks after discharge from hospital admission for the index event c (±14 days) FOR TEVAR+BMT+ SURV	6 months after randomisation (±30 days)	1 year and yearly to 5 years after randomisation. (±30 days)

Confidential Page 24 of 30

EARNEST	Protocol No:	Sponsor:	Imperial	College	V1.0 7 th Oct 2024
	174766	London			

		II.		Į.		
		index uTBAD, noting TEVAR must be performed in 3 months after index event		6 weeks after TEVAR ^c (±14 days)		
Inclusion & exclusion criteria	Х	X				
Informed consent		x				
Demography		X				
Medical history		X		X	x	x
Clinical assessment		x		x	x	x
Clinical details of uTBAD admission		x				
Blood pressure ^a		x	x	x	x	x
CTA aorta		Х		Xp		X
Site report of CT Aorta		X		X		X
Transfer of CT to core lab		X		X (six weeks after discharge from hospital after index event OR six weeks after TEVAR)		X, at 1 and 5 years only
EQ-5D-5L		X		x, measured before imaging results are relayed to the participant	x, measured before imaging results are relayed to the participant	x, measured before imaging results are relayed to the participant
Procedural details			X			
Health resource use, from NHS and personal and social care				x	x	х
Document re- intervention				X	X	x
Document adverse events			X	X	X	х

Confidential Page 25 of 30

EARNEST	Protocol No: 174766	Sponsor: London	Imperial	College	V1.0 7 th Oct 2024

^aStandardised BP measurement: This will be measured using standard protocols. At each visit, three BP recordings will be measured in the sitting position using a validated semi-automated device after at least ten minutes rest. The mean of the second and third readings will be used in analyses. Smoking or vaping will not be permitted for 30 minutes before BP measurement.

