4.5 Follow-up

Follow up visits will take place at each of the sites in a clinical examination room for interview, examination, BP readings and required questionnaires to be completed. Each study visit will be expected to take less than one hour including rest periods for the subject.

Data will be collected on electronic case report forms using a study database called Sealed Envelope which is a regulatory-compliant database and is sponsor-approved for non-CTIMP studies.

Participants will be consented for the central study team to access routinely collected healthcare data, confirming whether the patient has had additional procedures/hospital admissions during the follow up period. Consent will also allow for identifiable data to be linked with the national databases including the National Vascular Registry data, Hospital Episode Statistics data (in England), CHI data, Electronic Data Research and Information Service DRIS (in Scotland) and from the Office of National Statistics. The identifiable fields (NHS number) required for linkage will be encrypted using a one-way encryption algorithm. We will ask patients if they are happy to give consent for their health status to be followed up over time. This will be done by linking the patient's identifiable data with records held by the NHS and maintained by the NHS Information Centre and the NHS Central Register, or any applicable NHS information system. This will allow us to track what happens after the study finishes and observe if anyone gets further tests/investigations and treatment they may have.

As uTBAD may not develop for many years, we will also ask patients to give consent for us to keep personal data stored or accessed for 15 years on the NHSCR (National Health Service Care Register) so that data from national registries can be evaluated. For instance, long-term survival information to be flagged through national registries, for example NHS Digital (previously the Health and Social Care Information Centre); Office of National Statistics (ONS) in England/Wales; General Register Office in Scotland; Hospital Episode Statistics (HES) or Office for Health Improvement & Disparities

Confidential Page 26 of 30

^b If the participant has already undergone a scan at 6 weeks prior to randomization, ie. The patient has been randomised after 6 weeks from discharge, an additional clinical 6 week scan will not be required. All images should however be transferred to the core laboratory

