Overall: Assuming 2.5% cross-over from each arm (low estimated because TEVAR in the sub-acute phase can only occur between 10 days and 3-months), we would expect event rates of 16.85% (=17.11x0.975 + 6.83x0.025) in the TEVAR+BMT arm and 7.09% (=6.83x0.975 + 17.11x0.025) in the SURV+BMT arm. This corresponds to an average observed event rate over the two arms of 11.97% and a hazard ratio of approximately 0.4 for TEVAR+BMT, relative to SURV+BMT (estimated from hazards based on exponential time to event rates).

Using Stata v17.0 and command, (power cox, hratio(0.4) failprob(0.1197) effect(hratio) power(0.9)), for 90% power, and two-sided type-1 error 5%, we would require 51 events in 419 patients. Inflating this to allow 10% of patients to be lost to follow up (and censored at last visit in the primary analysis), we require 57 events in 470 patients (235 in each arm), followed up for 5 years (based on Cox regression for primary analysis). The estimand for our primary analysis is the hazard ratio for the comparison between TEVAR+BMT and SURV+BMT (see the separate Statistical Analysis Plan for full details of the methods for estimating the sample size).

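### The primary analysis censors event-free participants at their last visit, contradicting the protocol's own endpoint table, and sets no common cut-off for events and non-events

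*Protocol*

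**What the plan says.** **Censoring rule, stated twice.** Section 7.3 (Primary Endpoint Analysis) covers participants who have no event or are lost to follow-up: "including due to intercurrent events such as non-aortic death) will be censored at last visit". Section 7.1 repeats the rule for the 10% expected to be lost: "and censored at last visit in the primary analysis".

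**A different rule for the same endpoint.** The primary endpoint row of the table in section 1.9 reads: "Patients censored if there is a competing event (non-aortic-related death, patient withdrawal or end of the study". It does not mention the last visit. Section 1.7 runs the endpoint from randomisation to at least 5 years or to death from any cause.

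**Visits.** Section 2.1: "All patients will be seen at 6-weeks, 6-months, one year and yearly (to five years after enrolment". The schedule in section 4.4 agrees: "1 year and yearly to 5 years after randomisation".

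**Length of follow-up.** Section 2.1: "Each patient will be followed up for a minimum of 5-years". Section 7.3: "This primary analysis will take place when all participants are at least 5 years post-randomisation". Section 7.2 predicts 42 months of recruitment. The first recruits may therefore be about 5 + 3.5 = 8.5 years from randomisation at the primary analysis, with a last scheduled visit at year 5.

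**Sources of event information.** Section 1.7 sends site reports to a blinded adjudication committee. Section 6.2 records SAEs, which include deaths, throughout the study, and section 8.13 ends the trial at database lock rather than at the last visit. Section 4.5 adds registry linkage: "Consent will also allow for identifiable data to be linked with the national databases".

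**The concern.** A censoring date should mark when a participant stopped being observable, whatever happened to them next. Under section 7.3 it depends on the outcome. Take two people who attend the year-2 visit and die at 2.5 years. The aortic death is an event at 2.5 years. The non-aortic death is censored at 2.0 years, although that person was known to be alive and at risk for a further half year. Section 1.9 would censor the second person at 2.5 years.

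The same asymmetry is larger after year 5. An event-free participant stops at the year-5 visit, yet nothing stops an adjudicated death at, say, year 7 from counting. The risk set beyond year 5 would then contain only people who go on to have an event.

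At stake are the primary Kaplan-Meier curves and, under some readings, the primary hazard ratio. Section 7.3 uses similar survival methods for aortic-related mortality, all-cause mortality and reinterventions, so the rule may carry over to those.

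**Working it through.** **1. The plan's own figures.** Section 7.1 gives crossover-adjusted 5-year rates of 17.11 × 0.975 + 6.83 × 0.025 = 16.85% and 6.83 × 0.975 + 17.11 × 0.025 = 7.09%. That sentence attaches the arm labels the wrong way round; I take 16.85% as control. The exponential hazard ratio is ln(1 − 0.0709)/ln(1 − 0.1685) = 0.398. The Schoenfeld formula at HR 0.4, 90% power and two-sided 5% gives 50.06 events, rounded up to 51. Then 50.06/0.1197 = 418.2, so 419 patients, and 419/0.9 = 466 against the stated 470. The sample size reproduces, and this point does not affect it.

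**2. Hand calculation within 5 years.** Assume 10% loss (section 7.1) and 10% non-aortic death (my assumption) by 5 years, both exponential and equal by arm.

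- Hazards per year: loss and non-aortic death −ln(0.9)/5 = 0.0211 each; control events −ln(1 − 0.1685)/5 = 0.0369; TEVAR events 0.0147.
- Mean time at risk is (1 − e^(−5t))/t, where t is the sum of the three hazards: 4.13 years in control, 4.35 in TEVAR.
- Proportion censored early by loss or non-aortic death: 17.4% and 18.3%.
- Mean gap back to the previous visit on the protocol's grid (6 weeks, 6 months, years 1 to 5): about 0.44 years.
- Time discarded per person: 0.174 × 0.44 = 0.077 and 0.183 × 0.44 = 0.081 years.
- Hazard inflation: 4.13/(4.13 − 0.077) = 1.019 and 4.35/(4.35 − 0.081) = 1.019.

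The inflation is the same in both arms, so the hazard ratio cancels. Control incidence becomes 1 − exp(−5 × 0.0369 × 1.019) = 17.1% instead of 16.85%.

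**3. Simulation.** There were 2,000,000 patients per scenario, with exponential events at the section 7.1 rates and the protocol's visit grid. The third column also counts fatal events after loss to visits, taking deaths as 14.8/17.11 = 86.5% of control events and 5.39/6.83 = 78.9% of TEVAR events. Cells show 5-year KM (control / TEVAR) and HR. NAD is non-aortic death by 5 years.

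| Scenario | Exact-date censoring | Last visit | Last visit, plus deaths after loss |
|---|---|---|---|
| 5-year cut, loss 10%, NAD 5% | 16.85 / 7.12; 0.400 | 17.06 / 7.21; 0.400 | 17.74 / 7.50; 0.400 |
| 5-year cut, loss 10%, NAD 10% | 16.86 / 7.04; 0.395 | 17.15 / 7.16; 0.395 | 17.84 / 7.47; 0.395 |
| 5-year cut, loss 10%, NAD 20% | 16.85 / 7.09; 0.399 | 17.29 / 7.29; 0.399 | 17.99 / 7.59; 0.398 |
| 5-year cut, loss 15% control, 5% TEVAR, NAD 10% | 16.84 / 7.13; 0.402 | 17.21 / 7.23; 0.398 | 18.26 / 7.37; 0.381 |
| 5-year cut, loss 5% control, 15% TEVAR, NAD 10% | 16.85 / 7.09; 0.399 | 17.06 / 7.25; 0.403 | 17.38 / 7.71; 0.419 |
| Events to year 5-8.5, loss 10%, NAD 10% | 16.89 / 7.09; 0.397 | 17.18 / 7.22; 0.470 | 17.81 / 7.50; 0.474 |
| Events to year 5-8.5, no loss, no NAD | 16.77 / 7.12; 0.402 | 16.77 / 7.12; 0.485 | same as last visit |

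In the last two rows events count to an analysis date 0 to 3.5 years after year 5, while event-free participants stop at the year-5 visit. Kaplan-Meier incidence at 8 years then reads about 98% in both arms, against 25.5-25.7% and 11.1% with exact-date censoring.

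**4. Scale.** With 235 × 0.1685 = 39.6 and 235 × 0.0709 = 16.7 expected events, the standard error of the log hazard ratio is √(1/39.6 + 1/16.7) = 0.29. The shift from 0.402 to 0.381 is 0.053 on the log scale, about 0.2 standard errors.

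**The case against.** The strongest reply is that in the expected case little happens. The objective is framed over five years, the sample size assumes 5 years of follow-up, and every event-free completer has a last visit at year 5. Only the lost and the non-aortic deaths are affected. Step 2 confirms that the hazard ratio then cancels. This stands.

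A reader might infer that registry deaths are counted as primary events, so that the hazard ratio is biased as a matter of course. The protocol does not say so. Section 4.5 describes linkage for procedures, admissions and survival after the study, and section 1.7 routes endpoints through site reports. The results that count deaths after loss are therefore conditional. A reader might also infer that the curves will run to nearly 100% after year 5. That requires counting late events while ignoring the end-of-study censoring in section 1.9, which is one possible reading and not the stated plan.

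Two things survive the reply. First, sections 1.9 and 7.3 conflict whatever the size of the bias. Second, the harmless case is not the one specified: no 5-year cut is set, and SAE recording up to database lock allows sites to report later deaths without any linkage.

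Section 7.3 also plans inverse-probability-of-censoring weights and sub-distribution hazards. They show awareness of informative censoring and competing risks, but as described they leave the last-visit date in place. After year 5 no event-free participant would remain to be weighted.

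**Conclusion.** The point holds as an internal contradiction and a badly fixed censoring rule in the primary analysis. With equal 10% loss and non-aortic death of 5-20%, literal last-visit censoring raises 5-year Kaplan-Meier incidence by about 0.1 to 0.5 points. Counting deaths after loss to visits makes this about 0.4 to 1.1 points, and 1.4 in an arm losing 15%.

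The hazard ratio is essentially unchanged when loss is similar by arm and data stop at year 5. A loss split of 15% against 5% moves it by about 0.004, or about 0.02 if deaths after loss also count. The only material change, from 0.40 to about 0.47-0.49, occurs if events after the year-5 visit count while survivors stop there. The protocol does not exclude this, but does not state it either.

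The non-aortic death rates, the loss split and the uniform spread of follow-up after year 5 are assumptions. The event rates, the 10% overall loss, the visit grid and the 42-month recruitment are the protocol's.

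**What to change.** Reconcile sections 1.9, 7.1 and 7.3 into one rule, repeated in the SAP. Censor at whichever applies first:

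- the date of non-aortic death;
- the date of withdrawal;
- for those lost, the last date known from any source to be free of the composite endpoint;
- one common administrative cut-off, either 5 years from randomisation or a fixed calendar date.

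Apply that cut-off equally to events and non-events, and name it as the horizon of the primary hazard ratio. Count an event after loss to visits only if comparable event-free participants also contribute person-time over that interval.

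Do not simply run person-time for the composite to a linkage date. Linkage cannot supply the Barthel, NYHA or WHO components, so that would count time in which non-fatal events are unobservable. Limit that extension to the mortality endpoints or to a sensitivity analysis.

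The cost is a few sentences in three sections and matching SAP text, settled before outcome data are seen by arm. The sample size does not change, and a 5-year cut-off needs no new data collection.

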With conservative treatment of uTBAD, approximately 1/3 of patients develop late aneurysmal change with risk of rupture. Therefore, if fit, patients with known aortic expansion are offered an operation when the aorta reaches 5.5-6cm in diameter. These procedures are usually complex, extensive operations and carry a significant risk of death. The 30-day mortality rate in the effective treatment of thoracic aortic aneurysms (ETTAA) study was 6.7% after endovascular treatment and 11.1% after open surgery for chronic aneurysms of the aorta. Major complications such as paraplegia, stroke, myocardial infarction, respiratory failure and renal failure are frequent.[6, 7] The cost to the NHS is significant. In addition, the quality of life of patients under surveillance may be significantly impaired.

Confidential Page 14 of 30

EARNEST	Protocol No:	Sponsor:	Imperial	College	V1.0 7 th Oct 2024
	174766	London			

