4.6 Core Lab Evaluations

Anonymised DICOM CT data will be transferred to the core lab from site electronically or via CD. CT data from baseline (the first CT scan after the index uTBAD) at six weeks after discharge from hospital (after conservative management or after TEVAR) and at one year and five years after randomisation.

Data will be analysed according to a specific core lab protocol.

Incidental findings will potentially be identified on review of CT scans in the core lab. In each case the incidental finding will be reported to the principal investigator of the site and local protocol will determine the treatment of the individual.

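### The primary Cox model is valid, but baseline maximum aortic diameter, already available from the baseline CT, could be prespecified as a further covariate for a small gain at very low cost

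*Protocol*

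**What the plan says.** Protocol section 7.3, Primary Endpoint Analysis, specifies a Cox model "adjusting for minimisation variables age and sex as fixed effects and centres as random intercepts". These are exactly the factors used for minimisation in sections 2.1 and 4.3.

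Baseline diameter is neither a minimisation factor nor a covariate. It appears in the exploratory part of section 7.3: "We will explore the relationship between initial aortic diameter and changes over time".

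On availability, the visit schedule (section 4.4) places a CTA, its site report and transfer to the core lab at the baseline visit. Section 4.6 lists "CT data from baseline (the first CT scan after the index uTBAD") among the scans the core lab receives. Section 7.3 names the maximum diameter of the whole aorta among the core-lab measurements, and section 3.1 excludes dilatation above 5 cm.

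On relevance, section 1.1 states that about a third of conservatively treated patients develop late aneurysmal change with a risk of rupture, and that "patients with known aortic expansion are offered an operation when the aorta reaches 5.5-6cm in diameter". Section 5.1 says that untreated dilatation leads to rupture. Section 7.1 derives the late non-fatal part of the composite from the risk attached to late interventions.

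**The concern.** Diameter lies on the pathway that the protocol describes towards both aortic death and the complications of late repair, and these make up most of the primary composite. It is measured before randomisation, so adjusting for it introduces no bias.

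In a Cox model, leaving out a prognostic covariate pulls the estimated hazard ratio towards 1 and leaves any chance imbalance in that covariate uncorrected. With so few planned events, an imbalance could be raised against the result in either direction. Adding diameter after the data are seen would not be credible, so the choice has to be made in advance.

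**Working it through.** **1. The plan's own figure.** Section 7.1 uses "power cox, hratio(0.4) failprob(0.1197) effect(hratio) power(0.9"), with no term for covariates, and concludes "for 90% power, and two-sided type-1 error 5%, we would require 51 events in 419 patients".

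- Schoenfeld events: (1.960 + 1.282)² / (0.25 × (ln 0.4)²) = 50.06, so 51.
- Patients: 50.06 / 0.1197 = 418.2, so 419.
- Hazard ratio: ln(1 − 0.0709) / ln(1 − 0.1685) = 0.399.
- Loss, from "Inflating this to allow 10% of patients to be lost to follow up": 419 / 0.9 = 466 and 51 / 0.9 = 57, against the stated "we require 57 events in 470 patients (235 in each arm), followed up for 5 years". The difference between 466 and 470 is immaterial.

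The sample size reproduces without any gain from covariates.

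**2. Power with and without adjustment.** Simulation inputs from the protocol: 470 patients 1:1, five-year marginal risks held at 16.85% (BMT) and 7.09% (TEVAR), 10% loss, Wald test at two-sided 5%. The assignment of risks to arms follows the formulas in section 7.1, since the arm labels there are interchanged. The prognostic strength is not in the protocol and is assumed.

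Diameter alone, 9,000 runs per row (Monte Carlo standard error √(0.9 × 0.1 / 9,000) ≈ 0.3 points for each power):

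| HR per SD | Unadjusted | Adjusted | Mean log HR, unadjusted → adjusted |
|---|---|---|---|
| 1.5 | 89.9% | 90.5% | −0.94 → −0.95 |
| 2.0 | 89.1% | 91.0% | −0.94 → −0.97 |
| 2.5 | 89.7% | 93.2% | −0.94 → −1.00 |

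Diameter plus a second independent covariate (time since dissection), about 150,000 runs per row, about 53.5 events each. Two independent normal covariates act together like one with log HR √(a² + b²), where a and b are the two log HRs; the last column gives that equivalent:

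| HR per SD (diameter, time) | Unadjusted | Adjusted | Single-covariate equivalent |
|---|---|---|---|
| 1.0, 1.0 | 89.5% | 89.4% | 1.00 |
| 1.25, 1.1 | 89.6% | 89.7% | 1.27 |
| 1.5, 1.25 | 89.7% | 90.4% | 1.59 |
| 1.75, 1.25 | 89.6% | 90.9% | 1.83 |
| 2.0, 1.5 | 89.7% | 92.0% | 2.23 |
| 2.5, 1.5 | 89.7% | 93.6% | 2.72 |

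The two tables agree. For diameter alone the gain is about 0 to 1 point at 1.25 to 1.75 and about 2 to 4 points at 2.0 to 2.5. The treatment standard error barely moves (0.302 to at most 0.304). The gain comes from the estimated hazard ratio moving away from 1, from 0.396 down to between 0.394 and 0.365 in the rows with a prognostic effect.

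**3. Chance imbalance.** With 235 per arm, the SD of the between-arm difference in standardised diameter is √(2/235) = 0.092. A two-SD imbalance is therefore about 0.185. It shifts the unadjusted log HR by about 0.185 × ln 1.5 = 0.075, or 0.185 × ln 2.0 = 0.128. The second is 0.128 / 0.302 ≈ 0.4 of a standard error, and would move a hazard ratio of 0.40 to about 0.35 or 0.45.

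**4. Cost of missing values.** The primary analysis is complete-case (section 7.3, Sensitivity Analysis). If 5% of participants lacked a diameter, 51 × 0.95 ≈ 48.5 events would remain. Schoenfeld power is Φ(√(D × 0.25) × |ln 0.4| − 1.960), which gives 90.5% at D = 51 and about 89.0% at D = 48.5. A loss of 1.5 points would cancel the gain in all but the strongest scenarios, so a fallback rule is needed.

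**The case against.** The strongest objection is that nothing here is wrong. Adjusting for the minimisation factors is standard and internally consistent, and the stated power relies on no covariate gain. That stands.

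No section says that baseline diameter predicts the composite. Section 1.1 concerns diameter reached during follow-up, section 7.3 leaves the relation of initial diameter to later change for exploration, and the 5 cm exclusion narrows the range, which makes very strong effects harder to assume. That also stands, and it is why the lower part of the range deserves most weight.

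Adjustment is not wholly free. The hazard ratio becomes conditional on one more variable and its value shifts. This is a change of degree, because the planned hazard ratio is already conditional on age, sex and centre. The complete-case loss is largely avoided by falling back on the site-reported value, since applying the 5 cm exclusion already requires the size of the aorta to be known. The price is two measurement sources in one covariate. The core-lab baseline scan may also precede randomisation by up to about three months, which does not affect its validity as a covariate.

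A reader might infer that days since dissection should be added too. The protocol does not support that: sections 1.2 and 1.3 present timing as governing how well TEVAR remodels the aorta. That is modification of the treatment effect and not prognosis in both arms, and a main-effect term would not capture it.

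**Conclusion.** The primary model is valid. Adding baseline maximum aortic diameter is a small, low-cost improvement. Its size rests on an assumed prognostic strength: about 0 to 1 point of power at a hazard ratio per SD of 1.25 to 1.75, and about 2 to 4 points only at 2.0 to 2.5, under exponential times, a normally distributed covariate and 10% loss. If diameter has no prognostic value the cost is negligible: even two null covariates lower power only from 89.5% to 89.4%. Protection against chance imbalance is the further benefit.

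A reader might go further and conclude that power is being lost or that the trial is undersized. Neither follows. The loss cannot be shown without an effect size that the protocol does not give, and the 51 events in 419 patients reproduce without any covariate.

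**What to change.** Before any outcome data are seen, amend section 7.3 and carry the change into the SAP:

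- Add baseline maximum aortic diameter, continuous, as a fixed effect in the primary Cox model alongside age, sex and the centre random intercept.
- Use the core-lab value, and the site-reported CT value where no core-lab reading exists, so that no participant is dropped under the complete-case rule. Report how many values come from each source.
- Keep the model with age, sex and centre only as a supporting analysis.
- Do not add days since dissection as a main effect.

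The cost is wording, one extra parameter on about 51 to 57 events, a covariate with two measurement sources, and a hazard ratio conditional on one more variable. No new scan is needed and the sample size stays at 470.
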